5.0 Study Procedures

5.1 Study Design

- This is a single-blind, randomized, ascending dose escalation Phase I study of HF-LED-RL in healthy subjects with Fitzpatrick skin types I to III to evaluate safety of HF-LED-RL in Fitzpatrick skin types I to III (Figure 1). The study endpoint of 640 J/cm² is due to feasibility, as this dose corresponds to two hours of HF-LED-RL irradiation, and we anticipate decreased subject compliance with HF-LED-RL exposures longer than 2 hours in duration. The study endpoint of 640 J/cm² was also selected as this dose demonstrated increased anti-fibrotic properties in vitro compared to lower doses of HF-LED-RL (Mamalis 2015). Subjects will receive HF-LED-RL phototherapy or mock therapy three times a week for

three consecutive weeks, which is a standard phototherapy regimen based on phototherapy guidelines (Anderson et al 2015, Menter et al 2010, Zanolli et al 2004).

The HF-LED-RL light source is a commercially available Omnilux New-U hand-held LED-RL phototherapy unit (provided by Photo Therapeutics, Carlsbad, CA, USA), and is FDA-cleared for treatment of periorbital rhytides (crow's feet) with doses up to 160 J/cm². The temperature-matched mock therapy unit, also provided by Photo Therapeutics, Carlsbad, CA, USA, generates only heat output comparable to heat generated by the HF-LED-RL device, which is less than two degrees Celsius of heat output, and does not emit HF-LED-RL.

We do not classify erythema (redness) lasting less than 24 hours as an adverse event in our study, and is expected to occur in at least 10% of subjects as previously demonstrated in published studies (Sadick 2008, Sadick 2008). Common expected procedure outcomes include: warmth, erythema (redness), and edema (swelling) that is expected to last less than 24 hours.

- The maximum tolerated dose (MTD) is defined as the dose level below the dose producing unacceptable but reversible toxicity in two or more subjects ($\geq 20\%$) and is considered the upper limit of subject tolerance. If two or more subjects experiences any adverse event (including: first-degree or higher skin burning or blistering, erythema lasting more than 24 hours, swelling, pain, ulceration, infection, change in sensation, and/or

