muscle weakness), then this is the dose one above the MTD and we will not proceed with this dose or escalate the dose. The dose below the dose that generated the adverse event is the MTD. Rare but serious adverse events include second or higher degree skin burn, severe swelling, pain, ulceration, change in sensation, or muscle weakness leading to hospitalization, life-threatening events, or death.

The data safety monitoring board (DSMB) includes: [name], [name], and [name]

HF-LED-RL phototherapy and mock therapy at fluences of 480 J/cm² or 640 J/cm² will be administered to 65 subjects with Caucasian (white) skin types (Fitzpatrick skin types I, II, and III) to determine safety of HF-LED-RL at fluences of 480 J/cm² and 640 J/cm² in Fitzpatrick skin types I, II, and III. Because up to 320 J/cm² HF-LED-RL was found to be safe in all Fitzpatrick skin types (unpublished data from “previous Phase 1 LED-RL study”), this study will study 480 J/cm² and 640 J/cm² in Fitzpatrick skin types I, II, and III based on Spilker’s dose escalation protocol (X=160 J/cm², 2X=320 J/cm², 3X = 480 J/cm², and 4X = 640 J/cm²).

Number of subjects in each group:

Group 1 (480 J/cm²; 3 or 6 HF-LED-RL phototherapy subjects and 2 or 4 mock therapy subjects) - Total 5 or 10 subjects

Group 2 (640 J/cm²; 3 or 6 HF-LED-RL phototherapy subjects and 2 or 4 mock therapy subjects) - Total 5 or 10 subjects

Group 3 (480 or 640 J/cm² depending on dose escalation algorithm; 27 HF-LED-RL phototherapy subjects and 18 mock therapy subjects) - Total 45 subjects

* If there is one adverse event in one subject in either Group 1 or 2, five additional subjects will be added to that group (3 will receive HF-LED-RL and 2 will receive mock therapy).

We based our dose escalation protocol for this new study on a similar Phase 1 dose escalation study design outlined in the Journal of National Cancer Institute (Le Tourneau et al 2009), to determine dose escalation and to account for a possible outlier effect in the treatment group. Dose escalation starts at fluence of 480 J/cm² and continues up to fluence of 640 J/cm² until at least two subjects among a cohort of five to ten subjects experience an adverse event (i.e. $\geq 20\%$ of subjects with an adverse event at that dose level).

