Our dose-escalation protocol is as follows (Figure 2): In the first group (Group 1), HF-LED-RL phototherapy or mock therapy treatment time durations associated with 480 J/cm² will be administered to five subjects. Five subjects will be enrolled with three subjects randomized to HF-LED-RL phototherapy and two subjects randomized to mock therapy. Randomization is performed with website: www.randomizer.org. The randomizer will generate arabic numerals (e.g. “1”, “2,” “3”). Each enrolled subject will undergo two randomizations. For the first randomization, “1” is Group 1, “2” is “Group 2” and “3” is Group 3. 10 subjects will be

randomized to Group 1, 10 subjects will be randomized to Group 2, and 45 subjects will be randomized to Group 3. If there are no adverse events in the first five subjects of either Group 1 or 2, then the remaining 5 subjects of the 10 subjects randomized to that group will default into Group 3. For the second randomization, "1" is HF-LED-RL phototherapy and "2" is mock therapy. This study is single-blind and subjects will be blinded to this randomization, while researchers ([name], [name], and [name]) have knowledge of all subjects' randomization for the entirety of this study.

Dose escalation starts at fluence of 480 J/cm² and continues up to fluence of 640 J/cm² until at least two subjects among a cohort of five to ten subjects experience an adverse event (i.e. >20% of subjects with an adverse event at that dose level). If there are no adverse events in the five subjects treated with HF-LED-RL or mock therapy at fluence of 480 J/cm² in Group 1, then we will escalate the dose of HF-LED-RL or mock therapy to fluence of 640 J/cm² in the next cohort of five subjects (Group 2). If there is a single adverse event with HF-LED-RL or mock therapy at fluence of 480 J/cm², we will repeat the same dose of 480 J/cm² in a new cohort of five additional subjects (Group 1A). This is to account for a possible outlier effect. If two or more subjects in the first cohort of Group 1 experiences an adverse event with HF-LED-RL or mock therapy at fluence of 480 J/cm², then the study will stop and the MTD is 320 J/cm². If there are no adverse events in Group 1A, then the dose will be escalated to 640

J/cm2 in the next cohort (Group 2). If there is an adverse event in Group 1A ($\geq 20\%$), then the study will stop and the MTD is 320 J/cm2.

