After either a MTD has been established or the study endpoint of 640 J/cm2 has been achieved, an additional 27 HF-LED-RL phototherapy subjects (for a total of 30 or 33) and 18 mock therapy (for a total of 20 or 22) (determined randomly) will be enrolled to satisfy Hanley's Rule of Three, such that it can be concluded with 95% confidence that fewer than 1 person in 10 will experience an adverse event (Figure 3). (Hanley 1983) If the MTD is 320 J/cm2, then the study will be stopped and no further testing of the MTD of 320 J/cm2 in the larger cohort will be indicated because the MTD of 320 J/cm2 was already tested in a large cohort in the "previous Phase 1 LED-RL study". Of the larger expansion cohort, the study will be halted (stopped) if adverse events determined to be device related equals or exceeds 30%.

This clinical trial will be registered on <https://clinicaltrials.gov> following IRB approval and prior to subject enrollment.

- The subject will receive standard of care treatment in the dermatology clinic for any adverse event. Physical examination/visual inspection of the treated forearm will occur at every study visit. Treatment will be initiated, if indicated, for any procedural outcomes or adverse events noted at every study visit. Any general dermatology adverse events will be managed by [name] in the Dermatology clinic, per standard of care. If a skin ulcer occurs, we will record the skin ulceration as a superficial ulceration

(meaning it is nearly flush with the skin) or, if measurable, the depth of ulceration in millimeters. If skin ulceration occurs, we will consult [name], who is an expert in wound healing and head of the Sacramento VA wound clinic, for management. If change in sensation or muscle weakness occurs in a subject, the subject will be sent to Sacramento VA Emergency Room for urgent grading and management. If there are any other adverse events that cannot be managed in the Dermatology clinic, the subject will be sent to the Sacramento VA Emergency Room for urgent care.

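### The 30% halt for the expansion cohort names no arm, unit or checking time, and read literally its denominator includes 18 mock subjects who dilute it

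*Combined protocol and SAP*

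**What the plan says.** Section 5.1 (Study Design) sets the expansion halt in one sentence: "Of the larger expansion cohort, the study will be halted (stopped) if adverse events determined to be device related equals or exceeds 30" (percent). The same section describes Group 3 as "27 HF-LED-RL phototherapy subjects and 18 mock therapy subjects) - Total 45 subjects". Group 3 may grow: if the first five subjects of Group 1 or Group 2 have no adverse event, "then the remaining 5 subjects of the 10 subjects randomized to that group will default into Group 3".

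The escalation stage is more explicit. It counts subjects, in both arms: a cohort is repeated "If there is a single adverse event with HF-LED-RL or mock therapy", and escalation continues "until at least two subjects among a cohort of five to ten subjects experience an adverse event".

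The expansion's stated aim is counted on HF-LED-RL subjects. Section 5.1 adds "an additional 27 HF-LED-RL phototherapy subjects (for a total of 30 or 33") so that, by the rule of three, an adverse event rate of 1 in 10 or more can be excluded with 95% confidence.

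Section 5.6 plans adverse event frequencies by treatment group once all subjects have finished. Section 6.0 provides quarterly data safety monitoring board meetings and lets the principal investigator recommend protocol changes, with no numerical criterion.

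**The concern.** Three things needed to apply the halt are missing.

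- **Arm.** The sentence refers to the whole expansion cohort. If that is the denominator, 18 of 45 subjects receive no red light, and a problem caused by light has to be much more frequent in the HF-LED-RL arm before the overall figure reaches 30%.
- **Unit.** Each subject has nine treatment sessions. Fourteen events could come from 14 subjects or from two (9 + 5).
- **Timing.** No checking schedule is given, so two people applying the rule to the same data could reach different decisions.

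The protection of healthy volunteers in the largest stage of the trial is at stake. Section 2.0 also says the results would guide dosing in later studies, and 27 of the 30 or 33 HF-LED-RL subjects at the final dose come from this stage.

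**Working it through.** **Inputs from Section 5.1.** Halt at 30% or more; Group 3 = 45 = 27 HF-LED-RL + 18 mock; possible Group 3 sizes of 50 or 55 through the default rule.

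**Assumptions, since the documents give no figures.** Each subject counts once; all events are device related; accrual is in 3:2 blocks; true event rates and checking schedules are as shown.

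**The plan's own figure.** Rule of three: 3/30 = 10.0% (exact, 1 − 0.05^(1/30) = 9.5%); 3/33 = 9.1% (exact 8.7%). The aim reproduces for zero events among HF-LED-RL subjects.

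**Halt count, literal reading.** 0.30 × 45 = 13.5, so 14 subjects halt and 13 (28.9%) do not. If all 13 are on HF-LED-RL: 13/27 = 48.1% (exact 95% interval 28.7% to 68.1%). If Group 3 is 50, 0.30 × 50 = 15, leaving at most 14/30 = 46.7%. If it is 55, 0.30 × 55 = 16.5, so 17 halt, leaving at most 16/33 = 48.5%.

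**Halt count, HF-LED-RL denominator.** 0.30 × 9 = 2.7 → 3; 0.30 × 18 = 5.4 → 6; 0.30 × 27 = 8.1 → 9. At most 8/27 (29.6%) can occur without a halt.

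**Single look at full enrolment, mock 0%.** With X ~ Binomial(27, p), P(X ≥ 14) against P(X ≥ 9) is 0.014 against 0.42 at p = 0.30, and 0.14 against 0.82 at p = 0.40.

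**Repeated looks.** After each block, add the new binomial counts, remove every path with count/treated ≥ 0.30, and sum what is left at the end. With looks after 15, 30 and 45 the literal rule halts at 5 (4.5 rounded up), 9 and 14. Probability of not halting:

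| Rule and schedule | Mock rate | True rate 30% | True rate 40% |
|---|---|---|---|
| All 45, every five from the 10th | 0% | 0.70 | 0.43 |
| All 45, after 15, 30, 45 | 0% | 0.87 | 0.62 |
| All 45, every five from the 10th | 5% | 0.61 | 0.34 |
| All 45, after 15, 30, 45 | 5% | 0.79 | 0.51 |
| All 45, every five from the 10th | 10% | 0.52 | 0.26 |
| All 45, after 15, 30, 45 | 10% | 0.70 | 0.40 |
| HF-LED-RL only, after 9, 18, 27 | any | 0.33 | 0.09 |

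Under 3:2 accrual, 9, 18 and 27 HF-LED-RL subjects are the same moments as 15, 30 and 45 in all. The like-for-like contrast at 30% with mock 0% is therefore 0.87 against 0.33.

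**How likely is the extreme?** P(not halted and at least 13 of 27), mock 0%, under the two schedules for all 45: 0.003 and 0.007 at a true 30% rate; 0.013 and 0.035 at 40%.

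**Reaching the expansion at all.** The figures above are conditional on passing escalation. For one dose level with three HF-LED-RL subjects and mock 0%, the chance of passing is P0 + P1 × P0. At 30% this is 0.343 + 0.441 × 0.343 = 0.494. Jointly, passing and not being halted: 0.494 × 0.704 = 0.35, or 0.494 × 0.874 = 0.43.

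**The case against.** **Pooling may be deliberate, or may not be meant at all.** Section 2.0 includes a mock device because heat may itself cause adverse events, and escalation counts mock events. A both-arm halt is consistent with that, and mock events could be device related. Equally, the sponsor may have meant the HF-LED-RL arm alone. Both points stand: the whole-cohort denominator is the literal reading, not the only one, and a 0% mock rate flatters the concern. At a 10% mock rate the dilution is smaller but still there (0.52 or 0.70 not halted at a true 30% rate).

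**The schedules are assumed.** Subjects are examined and diaries reviewed at every visit, so a running check is a natural reading. Starting at the fifth subject instead of the tenth, with mock 0%, gives 0.65 at 30% and 0.39 at 40%. This moves the figures little. If events are counted instead of subjects, the halt may come sooner; that is a reason to state the unit.

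**Other safeguards exist.** The monitoring board and the investigator can act. That route is written but discretionary and has no threshold.

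**Two stronger readings do not hold.** A reader might infer that nearly half of the HF-LED-RL subjects could readily have events with no halt. The 13-of-27 case needs the literal denominator, no mock events and a favourable event order, and it is improbable at the rates tested. A reader might also infer that a dose whose expansion data reached the 20% escalation limit would still be declared safe. The documents do not support this. The 1-in-10 aim needs zero events in 30; one event in 30 already gives a one-sided 95% upper limit of 14.9%, so 6 of 27 would plainly miss it. The general sentence in Section 5.1 against proceeding after two affected subjects is not expressly confined to Groups 1 and 2, although the algorithm applies it to cohorts of five to ten. Figures 2 and 3 are not available to settle the matter.

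**Conclusion.** The concern holds as a defect in the halting rule. The rule lacks an arm, a unit and a checking time, and its literal form lets mock subjects dilute it. At a true HF-LED-RL rate of 30%, the literal rule fails to halt with probability 0.70 to 0.87 (mock 0%) or 0.52 to 0.70 (mock 10%), against 0.33 with an HF-LED-RL denominator. These figures rest on assumed rates and schedules, subjects as the unit, 3:2 accrual and a Group 3 of 45, and they are conditional on passing escalation. The finding does not extend to a claim that the plan would name an unsafe dose as safe. Re-applying the 20% limit to expansion data is an optional design choice, not a correction the documents require.

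**What to change.** Replace the halting sentence in Section 5.1 with wording such as:

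> Stop the expansion if at least 30% of Group 3 HF-LED-RL subjects treated so far have had one or more device-related adverse events (3 of 9, 6 of 18, 9 of 27), or if at least 30% of all Group 3 subjects treated so far have. Check at least after each 9 HF-LED-RL subjects.

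The second limb keeps mock (heat) events in the halt. In Section 5.6, add that expansion results will be reported by arm with exact 95% intervals and set against the 1-in-10 aim.

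**Cost.** Wording only, with no extra subjects. Section 5.1 says the researchers know every allocation, so counting by arm needs no unblinding. The price is a somewhat higher chance of stopping at a tolerable rate: for the HF-LED-RL limb about 0.055 at a true 10% rate and 0.15 at 15%, slightly more if mock events occur.

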5.2 Recruitment Methods

- The total number of participants approved for recruitment is 200.
- Potential subjects will be identified and recruited from the Sacramento VA Medical Center, Mather via discussion with [name], [name], and/or [name] in Dermatology Clinic or through subject interest from IRB-approved flyers posted at the Sacramento VA Medical Center.
- Flyer (Please see below and as separate attachment)

Inviting Veterans to Participate in a Clinical Trial Studying the Safety of Red Light On Skin!

The Dermatology Service is exploring the safety of a FDA-cleared red light device. To study the safety of red light, we are evaluating different treatment times using the device in healthy skin over a three-week period. We previously studied the safety of light in all skin types and this study is designed to investigate the effects of light on fair skinned individuals.

Would you like to:

- Help veterans and the population at large?
- Make a contribution to medical science?
- Help discover new treatments for skin disease?
- Get compensated for your time participating in this study?

PLEASE ASK US!

Who may participate?

- Veterans of any age, with Caucasian (white) skin that may burn easily.
- Veterans who have not participated in a Sacramento VA red light study previously.
- Veterans wanting to make a positive impact on others.

Where is this study?

- Building 801, Dermatology Clinic, Sacramento VA Medical Center, Mather

If you are interested in participating in this study or if you have any questions, please contact research coordinator:

[name]
[contact]

- Subjects will receive a prorated amount of compensation based upon the number of completed study visits. Subjects must complete two or three study visits in the week to receive payment for that week. If patients complete two study visits in a week, they will receive a prorated payment of \$33.33 for that week. If a subject completes three study visits in a week, they will receive a payment of \$50 for that week. Completion of week 1: \$50, week 2: \$50, and week 3: \$50. Patients will receive a check weekly and there will be no delay in receiving the payment. If a subject misses two or more study visits total, he/she will be discontinued from the study.

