- All procedures will occur in the Dermatology clinic at the Sacramento VA Medical Center (observed by [name], [name], and/or [name]), three times per week for three consecutive weeks for total of nine study visits. Subjects will be counseled regarding common expected procedure outcomes including warmth, erythema (redness) and edema (swelling), found to resolve within 24 hours in other studies. (Sadick 2008) Any adverse events that occur in office during or immediately after HF-LED-RL phototherapy or mock therapy session will be recorded by [name]. Subjects will be called on Mondays to serve as a reminder of upcoming study visits for the week.
- Subjects will record daily any adverse events that occur at home using a subject diary of adverse events. The study diary will be completed approximately every 24 hours from the time of completion of the study procedure. The subject diary will have instructions on the first page and a

chart on other pages for the subject to complete for every symptom noted at home (attached as separate document). The chart will have headers of 'Date,' 'Time Symptom Started,' 'Time Symptom Cleared,' 'Location,' 'Describe the Symptom,' 'Severity,' 'Things that Make it Better,' 'Things that Make it Worse,' 'Any Treatments Tried at Home,' and 'MD Initial'. If a subject notices any changes sooner than 24 hours, they are encouraged to note it in their subject diary as soon as possible. If there are no changes, subjects will write "There are no changes." Recording in a diary should take 0 minutes per day if there is no reportable change. It may take up to 3 minutes per day if there is a reportable change. If there are any reportable changes, subjects will describe reportable changes using the provided instructions and template. Prior to study procedure at every study visit, subjects will be asked about any adverse events that have occurred, including, but not limited to: erythema, blisters, swelling, pain, ulceration, infection, numbness, tingling, and weakness. Subject's diaries will also be reviewed prior to study procedure at every study visit. [name], [name], or [name] will initial in the 'MD Initial' area at every visit, certifying that one of the researchers has reviewed the subject diary at every study visit.

Study Timeline:

HF-LED-RL Phototherapy or mock therapy procedure times are as follows:

Group 1 (480 J/cm²; 3 or 6 HF-LED-RL phototherapy subjects and 2 or 4 mock therapy subjects) - 90 minutes

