5.7 Withdrawal of Subjects

- Subjects may be withdrawn from the research without their consent in the event of an adverse event that jeopardizes the subject's safety or subject's noncompliance (e.g. missing two or more study visits). In the event that subject's study participation has to be discontinued, the principal investigator will explain to the participant the reasons for termination.
- There are no consequences/penalties should a subject decide to withdraw from the research. The subject is encouraged to contact [name] for the end-of-study visit. End-of-study visit will include photograph of the treated forearm, physical examination of the treated forearm, and collection of the subject's study diary. Subjects will be instructed to notify their primary care physician or follow-up in Dermatology clinic if any questions or concerns arise after the end of the study.

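### The weekly payment threshold pays nothing for a one-visit week, so it withholds earned pay only from subjects who leave, contrary to the plan's own proration and no-penalty statements

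*Combined protocol and SAP*

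**What the plan says.** Section 5.2 (Recruitment Methods) opens its payment paragraph with a principle: "Subjects will receive a prorated amount of compensation based upon the number of completed study visits". It then sets a condition: "Subjects must complete two or three study visits in the week to receive payment for that week". Two amounts follow. For two visits, "If patients complete two study visits in a week, they will receive a prorated payment of" $33.33; for three, "If a subject completes three study visits in a week, they will receive a payment of" $50. Each of weeks 1 to 3 carries $50, so the maximum is $150. No payment is listed for the two Week 0 visits.

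The same paragraph ends with the attendance rule: "If a subject misses two or more study visits total, he/she will be discontinued from the study". Section 5.1 gives the procedure schedule as "three times per week for three consecutive weeks for total of nine study visits"; these are Visits 3 to 11 in the sample timeline.

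Section 5.7 (Withdrawal of Subjects) says of voluntary withdrawal: "There are no consequences/penalties should a subject decide to withdraw from the research". It also allows removal by the study team: "Subjects may be withdrawn from the research without their consent in the event of an adverse event that jeopardizes the subject's safety".

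**The concern.** A weekly threshold is not proration. It would matter little if it simply encouraged attendance among subjects who stay in the trial. Read with the two-missed-visits rule, it cannot do that: a subject who completes only one of a week's three visits has reached the limit in that week alone. The condition can therefore apply only to people who are leaving, including those the study team removes because of an adverse event.

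The least comfortable case is a subject who reacts after the first session of a week. Stopping there earns nothing for that week, and one further session earns $33.33. In a safety trial, payment should not be arranged so that the step falls at that point. Two things are at stake: agreement between the payment and withdrawal sections, and an avoidable financial reason to accept another exposure after a reaction.

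**Working it through.** **Inputs.** From Section 5.2: $50 for three visits in a week, $33.33 for two, nothing for one, and discontinuation at two missed visits in total. From Section 5.1: nine procedure visits, three in each of three weeks, and 65 subjects.

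**1. Reproduce the plan's figure.** Proration gives $50 × (visits completed ÷ 3). For two visits, $50 × 2/3 = $33.33, which matches the plan. For one visit, $50 × 1/3 = $16.67, where the plan pays $0.

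**2. Who can have a one-visit week?** Take every attendance history over nine visits, with participation ending at the second missed visit.

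- Completers have no miss or one miss: 1 + 9 = 10 histories.
- Discontinued subjects are defined by the positions of their two misses: 9 × 8 ÷ 2 = 36 histories.
- The total is 46.

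A one-visit week can arise only in the week of the second miss, in one of two ways:

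- Both misses fall in the same week and the second is at its third visit: 2 histories per week × 3 weeks = 6.
- The first miss was in an earlier week and the second is at the middle visit of the current week: 3 histories for week 2 plus 6 for week 3 = 9.

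That makes 6 + 9 = 15 of the 46 histories. All 15 are discontinued, and none of the 10 completers has a one-visit week.

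**3. Size for a subject who attends every visit and then stops.**

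| Stops after procedure visit | Total under the plan | Total pro rata | Shortfall |
|---|---|---|---|
| 1 (Visit 3) | $0 | $16.67 | $16.67 |
| 4 (Visit 6) | $50 | $66.67 | $16.67 |
| 7 (Visit 9) | $100 | $116.67 | $16.67 |

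At the other five early stopping points (after procedure visits 2, 3, 5, 6 and 8) the plan already pays pro rata. At the three points shown, one more session raises that week's pay from $0 to $33.33. Under per-visit payment the same step is from $16.67 to $33.33.

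**4. Incentive to continue that remains after the change.** This is $150 minus the amount already earned.

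- After procedure visit 1: $150 now, $133.33 under per-visit payment (89%).
- After procedure visit 4: $100 now, $83.33 (83%).
- After procedure visit 7: $50 now, $33.33 (67%).

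**5. Cost.** A one-visit week ends participation, so each subject can have at most one. The ceiling is $16.67 × 65 = $1,083.55, about $1,084.

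**The case against.** A reader might infer that the rule biases the trial towards fewer recorded adverse events. The documents do not support that as a finding. Section 5.1 has staff observe each procedure, photograph and examine the forearm, review the diary, and ask about specific symptoms before every procedure. Each affected session is a Monday one, with the next examination on Wednesday. Rewarding return could even improve event capture, since a subject who simply stops is only encouraged to attend an end-of-study visit (Section 5.7). No provision cuts payment for reporting an event, and removal after an event is discretionary. What could escape notice is mainly erythema that lasts beyond 24 hours but clears before Wednesday, or pain and sensory change that the subject does not disclose. That route is real, because Section 5.6 takes erythema duration from the diary, but nothing in the documents shows that payment affects it.

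A reader might also tie the rule to the safety conclusion of fewer than 1 person in 10. One event in 30 gives an exact one-sided 95% upper limit of 14.9%, against 9.5% for none. That shift follows from any single missed event, whatever the cause. It shows how fragile a zero-event conclusion is and cannot be charged to the payment rule.

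Other points on that side carry weight. Earlier weeks' cheques are kept and no clawback is stated, so the forfeiture is limited to one visit's pay. It is not a whole week's earned pay, because the other $33.33 would not have been earned under proration either. Per-visit payment leaves most of the financial reason to continue. The consent pages, which might explain the terms, are not in the available copy.

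None of this removes the inconsistency. One sentence promises proration and the next withholds it, and the withholding falls only on those who leave.

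**Conclusion.** The point holds as a minor one. The payment paragraph contradicts its own proration principle and, for subjects who choose to leave after the first visit of a week, the no-penalty statement in Section 5.7. The loss is $16.67 of a possible $150, at three of the eight early stopping points. It falls on anyone who stops there, whether because of a reaction or for another reason. The jump from $0 to $33.33 for one further session is an undesirable incentive for a subject with a reaction; any effect on reporting is a plausible inference only.

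The conclusion assumes the scheduled three-visit week. The documents do not say what happens if a week is shortened by rescheduling or clinic closure. It also depends on what a completed visit means, which the plan does not define, so it is unclear whether a subject who attends but does not undergo the procedure would be paid.

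**What to change.** In Section 5.2, replace the weekly threshold with $16.67 for each completed visit among the nine procedure visits (Visits 3 to 11), keeping $50 for a full week and the $150 maximum. Naming the nine visits avoids doubt about the two Week 0 visits.

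Add two sentences. First, a scheduled visit attended for assessment only, with the procedure withheld or declined because of a reaction, counts as completed for payment. Second, reporting an adverse event does not reduce payment. The first lets a subject with a reaction return, be examined and be paid without a further exposure, which also helps event capture. Neither sentence settles when a procedure should be withheld; that remains a clinical matter. Align Section 5.7 and the consent wording with the new text.

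Removing the threshold costs at most $16.67 per subject, about $1,084 if all 65 had a one-visit week. Paying for assessment-only visits may add to this for affected subjects, but always within the existing $150 maximum. The rest is protocol and consent wording through the IRB. Dose, schedule, stopping rules and analysis are unchanged.
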